7.10. NASH and Fibrosis Biomarkers

Change from baseline in markers of hepatic fibrosis and apoptosis include CK-18 (M30 and M65), PIIINP, TIMP-1, HA, and PRO-C3, will be analyzed according to Section 7.7 and pairwise comparisons in Section 7.6 using the efficacy analysis set.

7.11. Reverse T3 (rT3)

Change in rT3 and FT3/rT3 will be analyzed according to Section 7.7 and pairwise comparisons in Section 7.6 using the efficacy analysis set.

7.12. Fibrosis-4 (FIB-4) Score

The Fibrosis-4 (FIB-4) score helps to estimate the amount of scarring in the liver. The FIB-4 score is calculated as:

[Age (years)
$$\times$$
 AST (U/L)] \div [Platelet Count (10⁹/L) \times ALT (U/L)0.5].

Age at informed consent will be used. Lab values at each visit, from the same visit, will be used. The central lab calculation of FIB-4 will be used in analyses. The FIB-4 score will be calculated at baseline, Week 6, Week 12, and Week 16.

The change from baseline in FIB-4 score will be analyzed in the same manner as specified in Section 7.7 and pairwise comparisons in Section 7.6 using the efficacy analysis set.

7.13. Enhanced Liver Fibrosis (ELF) Score

The enhanced liver fibrosis (ELF) score will be calculated as:

$$2.278 + 0.851 \ln (HA) + 0.751 \ln (PIIINP) + 0.394 \ln (TIMP-1)$$
.

Lab values from the same visit will be used to calculate the ELF score. The central lab calculation of ELF will be used in analyses. Programming will also calculate the score programmatically for validation. The ELF score will be calculated at baseline and post-baseline visits Week 6 and Week 12.

Final, Version 2.0, 26JULY2023

CONFIDENTIAL

The change from baseline in ELF score will be analyzed in the same manner as specified in Section 7.7 and pairwise comparisons in Section 7.6 using the efficacy analysis set.

7.14. Nonalcoholic Fatty Liver Disease (NAFLD) Fibrosis Score

The Nonalcoholic Fatty Liver Disease (NAFLD) fibrosis score will be calculated as:

```
-1.675 + [0.037 \times Age (years)] + [0.094 \times BMI (kg/m2)] + [1.13 \times baseline diabetes status (yes = 1, no = 0)] + [0.99 \times AST/ALT ratio] - [0.013 \times Platelet Count (109/L)] - [0.66 \times Albumin (g/dL)].
```

Age at informed consent and baseline diabetes status will be used. BMI at Screening, Baseline, and Weeks 6, 12, and 16 will be calculated using the weight from that visit and height from screening. Programming will calculate the score at each to be used in analyses. The NAFLD fibrosis score will be calculated at screening, baseline, Week 6, Week 12, and Week 16.

The change from baseline in NAFLD fibrosis score will be analyzed in the same manner as specified in Section 7.7 and pairwise comparisons in Section 7.6 using the efficacy analysis set.

7.14.1.1. AST to Platelet Ratio Index (APRI)

The AST to Platelet Ratio Index (APRI) will be calculated as:

```
(AST Level [IU/L] / AST Upper Limit of Normal IU/L]) \times 100 / Platelet Count (10^9/L).
```

Lab values at each visit, from the same visit, will be used. The APRI will be calculated at baseline, Week 6, Week 12, and Week 16.

The change from baseline in APRI will be analyzed in the same manner as specified in Section 7.7 and pairwise comparisons in Section 7.6 using the efficacy analysis set.

7.15. FAST Score

The change from baseline in the FAST score will be analyzed as described in Section 7.7 and pairwise comparisons in Section 7.6 using the efficacy analysis set.

The FAST score was calculated according to the following formula 10:

$$FAST = \{ exp \ (-1.65 + 1.07 \times ln \ (LSM) + 2.66 \times 10 - 8 \times CAP3 - 63.3 \times AST - 1) \} / \{ 1 + exp \ (-1.65 + 1.07 \times ln \ (LSM) + 2.66 \times 10 - 8 \times CAP3 - 63.3 \times AST - 1) \}.$$

CONFIDENTIAL

7.16. TE and CAP

The change from baseline in TE and CAP will be analyzed as described in Section 7.7 and pairwise comparisons in Section 7.6 using efficacy analysis set.

7.17. Pharmacokinetic Analyses

PK Parameter Generation:

The following PK parameters will be determined where possible from the plasma concentrations of TERN-501, TERN-101, and TERN-101 metabolite TRN-000971 using noncompartmental methods in validated software program Phoenix WinNonlin (Certara, Version 8.3.5 or higher) for all patients for the PK Sub-study Analysis Set:

CONFIDENTIAL

CONFIDENTIAL
Protocol Reference: TERNCB-2002

Table 8 PK Profile Day 1*

Parameter	Units ^a	Definition
AUC _{0-last}	h*ng/mL	area under the concentration-time curve from time 0 to the time of the last quantifiable concentration $(t_{last})^c$
AUC _{tau}	h*ng/mL	area under the concentration-time curve over a dosing interval (τ)
$\mathrm{AUC}_{0\text{-}\infty}$	h*ng/mL	area under the concentration-time curve from time 0 extrapolated to infinity ^c
%AUC _{extrap}	%	percentage of area under the concentration-time curve due to extrapolation from the last quantifiable concentration to infinity
C_{max}	ng/mL	maximum observed concentration
C_{tau}	ng/mL	concentration observed at the end of the dosing interval/immediately prior to dosing
T_{max}	h	time of the maximum observed concentration
T_{last}	h	time of the last quantifiable concentration
$t_{1/2}$	h	apparent terminal elimination half-life
CL/F	L/h	apparent total clearance (parent analyte only)
V_z/F	L	apparent volume of distribution during the terminal phase (parent analyte only)
$MR_{\text{ AUC0-}\tau}$		metabolite:parent ratio based on AUC _{0-τ}
$AUC_{0\text{-tau}}\!/\!D$	h*ng/mL/mg	AUC _{0-τ} normalized by dose administered ^d
$AUC_{0\text{-last}}\!/D$	h*xg/mL/xg	AUC _{0-tlast} normalized by dose administered ^d
$AUC_{0\text{-}\infty}\!/D$	h*ng/mL/mg	AUC _{0-∞} normalized by dose administered ^d .
C_{max}/D	ng/mL/mg	C _{max} normalized by dose administered ^d

^a Units are based on concentration units (provided by the bioanalytical lab or preferred units for presentation of PK parameters) and dose units used in the study.

^b The AUC will be calculated using the linear trapezoidal rule for increasing concentrations and the logarithmic rule for decreasing concentrations (linear up/log down rule).

^c Based on the last observed quantifiable concentration

^d Calculated by dividing the parameter by the dose (mg)

^{*} Concentration-time profile following dosing on Profile Day 1

Statistical Analysis Plan CONFIDENTIAL Labcorp Drug Development Study: 000000231152 Protocol Reference: TERNCB-2002

Table 9 PK Profile Week 12*

Parameter	Unitsa	Definition
AUC _{0-last}	h*ng/mL	area under the concentration-time curve from time 0 to the time of the last quantifiable concentration $(t_{last})^b$
$AUC_{tau} \\$	h*ng/mL	area under the concentration-time curve over a dosing interval (τ)
C_{max}	ng/mL	maximum observed concentration
C_{tau}	ng/mL	concentration observed at the end of the dosing interval/immediately prior to dosing
T_{max}	h	time of the maximum observed concentration
$T_{last} \\$		
$t_{1/2}$	h	apparent terminal elimination half-life
CL/F	L/h	apparent total clearance (parent analyte only)
V _z /F	L	apparent volume of distribution during the terminal phase (parent analyte only)
$MR_{\text{AUC0-tau}}$		metabolite: parent ratio based on AUC _{0-tau}
AR_{AUC}		accumulation ratio based on AUC _{0-tau}
AR_{Cmax}		accumulation ratio based on C _{max} during the dosing interval
$AUC_{0\text{-tau}}\!/D$	h*ng/mL/mg	AUC _{0-τ} normalized by dose administered ^d
$AUC_{0\text{-last}}\!/\!D$	h*ng/mL/mg	AUC _{0-tlast} normalized by dose administered ^d
C _{max} /D	ng/mL/mg	C _{max} normalized by dose administered ^d
LR		Linearity ratio

The dosing interval τ is 24 hours.

Additional PK parameters may be determined where appropriate.

Pharmacokinetic analysis will be carried out where possible using actual dose administered and actual postdose blood sampling times. If an actual time is missing, the sample concentration result will be treated as missing unless there is scientific justification to include the result using the nominal time.

^a Units are based on concentration units (provided by the bioanalytical lab or preferred units for presentation of PK parameters) and dose units used in the study.

^b Area under the concentration-time curve will be calculated using the linear trapezoidal rule for increasing concentrations and the logarithmic rule for decreasing concentrations (linear up/log down rule).

^c Based on the last observed quantifiable concentration

^d Calculated by dividing the parameter by the dose (mg)

^{*} Concentration-time profile following multiple dosing on Profile Week 12

The parameters C_{max} , C_{tau} , t_{last} , and t_{max} will be obtained directly from the concentration-time profiles. If C_{max} occurs at more than 1 timepoint, t_{max} will be assigned to the first occurrence of C_{max} .

The metabolite: parent ratio(s) (MR_{AUC}) will be calculated as follows:

 $MR_{AUC} = (AUC TRN-000971 / MW TRN-000971) / (AUC TERN-101 / MW TERN-101), where MW is the molecular weight of each analyte.$

The molecular weights of parent analyte and metabolite(s) to be used in the adjustment are as follows:

TERN-101 = 540.44 g/mol

TRN-000971 = 716.56 g/mol

The parameter $AUC_{0\text{-tlast}}$ or other common partial area may be used to determine MR_{AUC} if $AUC_{0\text{--}\infty}$ or $AUC_{0\text{--}\tau}$ cannot be reliably calculated for the majority of subjects.

The linearity ratio (LR) will be calculated as ratio of $AUC_{0-\tau}$ following multiple dosing to $AUC_{0-\infty}$ following a single dose:

 $LR = AUC_{0-\tau}$ Profile Week 12 / $AUC_{0-\infty}$ Profile Day 1

7.17.1. Criteria for the Calculation of Apparent Terminal Elimination Rate Constant and Half-life

The start of the terminal elimination phase for each subject will be defined by visual inspection and generally will be the first point at which there is no systematic deviation from the log-linear decline in concentrations.

The apparent terminal elimination rate constant (λz) will only be calculated when a reliable estimate can be obtained using at least 3 data points, preferably not including C_{max} , and the adjusted coefficient for determination of exponential fit (R^2 -adj) of the regression line is \geq 0.7. Parameters requiring λz for their calculation (eg, $AUC_{0-\infty}$, $t_{1/2}$, CL/F (Profile Day 1 only), Vz/F) will only be calculated if the R^2 -adj value of the regression line is \geq 0.7.

The following regression-related diagnostic PK parameters will be determined where possible:

CONFIDENTIAL

Labcorp Drug Development Study: 000000231152 Protocol Reference: TERNCB-2002

Parameter	Units	Definition
λ_z	1/h	apparent terminal elimination rate constant
λ_z Upper	h	end of exponential fit
λ_z Lower	h	start of exponential fit
$\lambda_z N$		number of data points included in the log-linear regression
λ_z Span Ratio		time period over which λ_z was determined as a ratio of $t_{1/2}$
R ² -adj		adjusted coefficient for determination of exponential fit

Where possible, the span of time used in the determination of λ_z (i.e., the difference between λ_z Upper and λ_z Lower) should be ≥ 2 half-lives. If the λ_z Span Ratio is < 2, the robustness of the $t_{1/2}$ values will be discussed in the clinical study report (CSR).

7.17.2. Criteria for Calculation and Reporting of Area Under the Concentration-time Curve

The minimum requirement for the calculation of AUC will be the inclusion of at least 3 consecutive concentrations above the lower limit of quantification. If there are only 3 consecutive concentrations, at least 1 should follow C_{max} . An exception may be made for metabolite, where C_{max} may be the last timepoint.

If the extrapolated area is >20%, AUC_{0- ∞} (and derived parameters) may be excluded from the summary statistics at the discretion of the sponsor or pharmacokineticist.

If the τ PK blood sample is collected slightly early (i.e., the 24 hours sample), the actual sampling time of the τ sample may be used for the calculation of AUC_{0- τ}. However, the AUC_{0- τ} parameter will be calculated if the τ sample is within 60 minutes of the nominal sampling time.

7.17.3. Criteria for Handling Concentrations Below the Limit of Quantification or Missing Concentrations for Pharmacokinetic Analysis (i.e., PK Parameter Generation)

For the purposes of PK parameter generation, plasma concentrations below the limit of quantification (BLQ) will be assigned a value of 0 before the first measurable concentration and thereafter BLQ concentrations will be treated as missing. The following rules apply to the specific situations defined below:

- If an entire concentration-time profile is BLQ, it will be excluded from PK analysis.
- Where there is NR, these will be set to missing.
- Where 2 or more consecutive concentrations are BLQ at the end of a profile, the profile will be deemed to have terminated and any further quantifiable concentrations will be set to missing for the calculation of the PK parameters, unless they are

CONFIDENTIAL

considered to be a true characteristic of the profile of the drug. If a predose plasma concentration is missing, it will be set to 0 by default within Phoenix WinNonlin for the first dosing day (Study Profile Day 1).

• For multiple dose (Study Profile Week 12), if the analyte concentration at τ (i.e., 24 hours postdose for once daily dosing) is missing, this may be substituted with the predose concentration. Similarly, if the predose concentration is missing then this may be substituted with the concentration at τ.

7.17.3.1. Treatment of Outliers in Pharmacokinetic Analysis

If a value is considered to be anomalous due to being inconsistent with the expected PK profile, it may be appropriate to exclude the value from the PK analysis. However, the exclusion of any data must have strong justification and will be documented in the CSR.

Any quantifiable predose concentration value on the first dosing day (Study Profile Day 1) will be considered anomalous and set to missing for the PK analysis if determined as predose after investigation. This will be set to 0 by default in Phoenix WinNonlin.

7.17.4. Presentation of Pharmacokinetic Data

A listing of PK blood sample collection times as well as plasma concentrations will be presented for TERN-501, TERN-101, and TERN-101 metabolite TRN-000971 separately for all patients for the Pharmacokinetics Analysis Set.

Pharmacokinetic concentrations will be summarized for the PK Analysis Set for each timepoint by treatment group using protocol scheduled times and appropriate summary statistics. Individual patient and geometric mean concentration-time profiles, for each TERN-101 dose, will be presented graphically on linear and logarithmic concentration scales for PK/PD substudy patients for Day 1 and Week 12.

If the actual time of sample collection deviates from the nominal time by more than $\pm 10\%$, the plasma concentration will be flagged and excluded from the summary statistics. Individual concentrations deemed to be anomalous will be flagged in the listings and excluded from the summary statistics. For plasma concentration data, the following rules will apply:

- Values that are BLQ will be set to 0 for the calculation of summary statistics and the number of values that are BLQ will be presented.
- Arithmetic mean or median values that are BLQ will be presented as 0.
- Where there is NR, these will be set to missing

CONFIDENTIAL

• If there are less than three values in the data series, only the minimum, maximum, and number of observations will be presented. The other summary statistics will be denoted as not calculated (NC). BLQ is considered a value for these purposes.

• If all values are BLQ, then the arithmetic mean, arithmetic SD, median, minimum, and maximum will be presented as 0, and the geometric mean and geometric CV% will be denoted as NC.

For PK parameters, the following rule will apply:

Geometric mean and coefficient of variation will not be calculated for T_{last} or T_{max}.

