Appendix 2: Sample Collection for Pharmacokinetics and Pharmacodynamics

Table 8 presents a description of PK/PD sample requirements at each study visit and timepoint.

Week	Day	Timepoint	Sample Type
0	1	Pre-dose (All Patients)	 Patients in PK/PD sub-study TERN-501, TERN-101, and TERN-101 metabolite TRN-000971 PK samples (PK/PD sub-study) Lipid Panel, 7αC4, FGF19, bile acids, and SHBG PD samples (PK/PD sub- study) Patients not participating in PK/PD sub- study Lipid Panel, 7αC4, bile acids, and SHBG PD samples
		 Post dose at the following timepoints (PK/PD sub-study only): 1 hour ± 5 minutes 2 hour ± 15 minutes 4 hours ± 15 minutes 6 hours ± 15 minutes 24 hours ± 1 hour prior to dosing on Day 2 	 TERN-501, TERN-101, and TERN-101 metabolite TRN-000971 PK samples 7αC4 and FGF19 PD samples
2	15 ± 3	Pre-dose (All Patients)	 TERN-501, TERN-101, and TERN-101 metabolite TRN-000971 PK samples Lipid Panel, 7αC4, and SHBG PD samples
4	29 ± 3	 Pre-dose (All Patients – PD samples) One sample between 2 and 6 hours post dose (All Patients – PK samples) 	 Lipid Panel, 7αC4, and SHBG PD samples TERN-501, TERN-101, and TERN-101 metabolite TRN-000971 PK samples
6	43 ± 3	Pre-dose (All Patients)	 TERN-501, TERN-101, and TERN-101 metabolite TRN-000971 PK samples Lipid Panel, 7αC4, and SHBG PD samples
8	57 ± 3	Pre-dose (All Patients)	TERN-501, TERN-101, and TERN-101 metabolite TRN-000971 PK samples
12	85±3	Pre-dose (All Patients)	 Patients in PK/PD sub-study TERN-501, TERN-101, and TERN-101 metabolite TRN-000971 PK samples Lipid Panel, 7αC4, FGF19, bile acids, and SHBG PD samples

Table 8PK/PD Sampling Timepoints

			 Patients not participating in PK/PD substudy TERN-501, TERN-101, and TERN-101 metabolite TRN-000971 PK samples Lipid Panel, 7αC4, bile acids, and SHBG PD samples
		 Post dose at the following timepoints (PK/PD sub-study only): 1 hour ± 5 minutes 2 hour ± 15 minutes 4 hours ± 15 minutes 6 hours ± 15 minutes 24 hours ± 1 hour on Day 86 PK only: 48 hours ± 2 hours on Day 87 72 hours ± 4 hours on Day 88 	 TERN-501, TERN-101, and TERN-101 metabolite TRN-000971 PK samples 7αC4 and FGF19 PD samples (up to 24 hours ± 1 hour on Day 86 only)
ET	ET	• At the ET Visit, for all patients discontinuing the study at any time for any reason (Early Termination)	 TERN-501, TERN-101, and TERN-101 metabolite TRN-000971 PK samples Lipid Panel, 7αC4, FGF19, bile acids, and SHBG PD samples

PD Sample Collection

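### The SAP's ±10% timing rule drops some protocol-compliant 2 h PK samples from the concentration summaries and is undefined for Week 4 and pre-dose samples

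*SAP*

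**What the plan says.** SAP 7.17.4 summarises plasma concentrations "for each timepoint by treatment group using protocol scheduled times and appropriate summary statistics". It then sets a timing filter that begins "If the actual time of sample collection deviates from the nominal time by more than" and puts the limit at 10% either way. The consequence of breaching that limit is that "the plasma concentration will be flagged and excluded from the summary statistics". The filter has no exception for pre-dose or sparse samples and does not mention the protocol's sampling windows.

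Protocol Appendix 2, Table 8 gives those windows as absolute times. For the sub-study they include "1 hour ± 5 minutes", "2 hour ± 15 minutes", "4 hours ± 15 minutes" and "6 hours ± 15 minutes". The later samples are allowed 1 hour either side at 24 h, 2 hours at 48 h and 4 hours at 72 h.

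Two kinds of sample have no numeric scheduled time. The Week 4 PK draw is described as "One sample between 2 and 6 hours post dose". The pre-dose samples are labelled only as pre-dose, with no clock offset or window.

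**The concern.** A percentage tolerance and an absolute window agree only by chance, and at an early sampling time the percentage can be the tighter of the two. A site that follows Table 8 exactly could then have valid concentrations removed from the tables.

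A percentage also needs a single non-zero nominal time. Without one, two programmers could apply the same sentence and produce different tables.

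The sparse samples matter because about 98 of the 140 patients (140 − 42) are outside the intensive sub-study. SAP 7.17 derives PK parameters only for the sub-study set. For the other patients, the by-arm concentration summaries are the only summarised PK that the SAP specifies. About 84 of the 98 would be on active drug (6 active arms × 14); Protocol 6.4 says placebo samples are not assayed.

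**Working it through.** The ±10% is a stated rule, not a derived figure, so there is nothing to reproduce. The check sets it against the protocol's windows.

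**Fixed post-dose times.** Inputs: windows from Protocol Table 8; tolerance from SAP 7.17.4.
- Window as a percentage = window ÷ nominal time.
- SAP tolerance = 0.10 × nominal time.
- Share of compliant times excluded, if evenly spread = 1 − tolerance ÷ window, or 0 where the tolerance is the larger.

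| Nominal | Protocol window | Window as % | SAP tolerance | Compliant share excluded |
|---|---|---|---|---|
| 1 h | ±5 min | 8.3% | ±6 min | 0 |
| 2 h | ±15 min | 12.5% | ±12 min | 1 − 12/15 = 20% |
| 4 h | ±15 min | 6.25% | ±24 min | 0 |
| 6 h | ±15 min | 4.2% | ±36 min | 0 |
| 24 h | ±1 h | 4.2% | ±2.4 h | 0 |
| 48 h | ±2 h | 4.2% | ±4.8 h | 0 |
| 72 h | ±4 h | 5.6% | ±7.2 h | 0 |

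Only 2 h conflicts. With about 6 sub-study patients per arm (Protocol 4.1), 20% is 0.20 × 6 = 1.2 values per arm on each of the two profile days.

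**Week 4 sample.** The documents give no single nominal time. Suppose one, t hours, were assigned. The kept range runs from the larger of 2 and 0.9t to the smaller of 6 and 1.1t, and the share of the 4-hour interval excluded is 1 − (kept width ÷ 4).
- t = 2: 2.0 to 2.2 h kept, 95% excluded.
- t = 3: 2.7 to 3.3 h kept, 85% excluded.
- t = 4: 3.6 to 4.4 h kept, 80% excluded.
- t = 5: 4.5 to 5.5 h kept, 75% excluded.
- t = 5.45: about 4.91 to 6.0 h kept, 72.7% excluded (the minimum).
- t = 6: 5.4 to 6.0 h kept, 85% excluded.

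So any single nominal time removes about 73% to 95% of an evenly spread interval. If the interval itself is the scheduled time, nothing inside it is excluded.

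**Pre-dose samples.** With nominal time 0, the deviation as a percentage is division by zero, and 10% of 0 is 0 minutes. Measured instead from the previous dose with nominal 24 h, the tolerance is 0.10 × 24 = 2.4 h, so 21.6 to 26.4 h is kept. The Day 1 pre-dose sample has no previous dose, so neither basis works for it.

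**The case against.** The strongest reply is that the documents support sensible readings wherever the rule looks severe.

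- **Week 4.** SAP 7.17.4 works from the protocol's scheduled times, and the scheduled time of this sample is the 2 to 6 h interval. On that reading a compliant sample has no deviation. A reader might infer that most Week 4 samples are lost. The documents do not support that, because the loss appears only after assigning a point nominal time that neither document gives.
- **Pre-dose.** A reader might infer that every pre-dose sample fails. An undefined percentage is not a failure. Protocol 8.2 has the time of the last dose before each PK sample recorded, the SAP defines Ctau as an end-of-interval or pre-dose concentration, and SAP 7.17.3 lets the Week 12 pre-dose and 24 h values stand in for each other. All of this points to about 24 h after the prior dose, where troughs near 24 h are kept.
- **Consequence.** A reader might infer that the by-arm concentration tables are emptied. They are not: six of the seven fixed post-dose times are untouched, listings retain every value, and the PK endpoints (AUC, Cmax, Ctau) are derived from actual times under SAP 7.17.
- **Remedy.** Simply substituting the Table 8 windows would tighten the tolerance at 1, 4, 6, 24, 48 and 72 h. A sample 20 minutes late at 6 h, kept now, would be dropped.

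All four points stand as limits on the finding. They do not remove it. The 2 h conflict depends on no reading. For the other samples, the SAP does not say which reading it adopts. The 24 h reading is also incomplete: the instruction to dose about 24 h before the visit covers only the sub-study's Week 12 visit, and Protocol 6.8 lets a forgotten dose be taken later the same day.

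**Conclusion.** The concern holds in a limited form.

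- **Definite conflict.** At 2 h the SAP tolerates 12 minutes and the protocol allows 15, so compliant samples between those limits are excluded from the concentration summaries. The size is 20% of the window, or about one value per arm per profile day, assuming evenly spread times. Times clustered near nominal would lose fewer.
- **Undefined rule.** For the Week 4 and pre-dose samples the finding is that the rule cannot be applied as written, not that it removes them. The 73% to 95% range shows what a poor programming choice would cost; it is not a prediction.
- **Reach.** Only descriptive concentration summaries are affected, and the PK objective is exploratory. No efficacy or safety analysis and no derived PK parameter depends on the rule. The point is minor, but worth correcting because the contradiction is plain and the correction costs almost nothing.

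**What to change.** Amend the timing rule in SAP 7.17.4 as follows:

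1. **Fixed post-dose times:** exclude a concentration from the summaries only if it lies outside both the Table 8 window and ±10% of nominal, so that the wider limit applies. This gives ±15 minutes at 2 h and leaves the other six times as they are now.
2. **Week 4:** state that the scheduled time is the 2 to 6 h interval, summarise it as one timepoint, and exclude no sample inside it on timing.
3. **On-treatment pre-dose samples:** require that the sample precedes that day's dose and falls within a stated time since the recorded prior dose, for example 24 h ± 10%.
4. **Day 1 pre-dose:** exempt from the timing rule.

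The cost is a few sentences and the matching programming; no new data are needed, since dose and sample times are already recorded. The downside is slightly more timing spread in the 2 h summary. The wording should be settled before unblinding so that the choice cannot depend on the results.

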Treatments in all cohorts were overall safe and well-tolerated. No deaths, serious AEs, or withdrawals due to AEs were reported in the study. In Part A (SAD) and Part B (MAD), no predefined study or study drug stopping criteria or dose escalation stopping criteria were met. Frequent vital signs and 12-lead ECG collection in the SAD and MAD cohorts revealed no remarkable findings. In Part A (SAD cohorts), all AEs were mild or moderate in severity, and no clinically meaningful changes or trends were seen in clinical laboratory parameters after singledose administration of TERN-501 up to 60 mg. In Part B (MAD cohorts), all AEs were mild in severity. Thyroid axis test findings appeared consistent with peripheral thyroid hormone modulation with lowering of free T4 without changes in free T3 or TSH, which were highly variable. ALT and AST values were also highly variable, but overall similar across the treatment groups; no subject who received TERN-501 had $ALT \ge 2x$ ULN and no subject with elevated ALT (i.e., > 2x baseline) had an associated increase in bilirubin levels. GGT mean values over time were generally similar to placebo for 1 mg, 3 mg, and 6 mg TERN-501 groups, and changes were not significantly different from placebo at Day 15 for these dosing groups. GGT increases for 10 mg TERN-501 were significantly higher than placebo throughout the treatment period, although values remained below the ULN. No apparent changes or trends were seen in ALP or total bilirubin levels over time. Total testosterone increases seen at doses > 3 mg TERN-501 appear to be dose-dependent and can be explained by increases seen in SHBG, reflecting THR- β agonist target engagement. Free testosterone and other sex hormones including estradiol, FSH, and LH remained largely unchanged. No clinically meaningful changes were observed in other clinical laboratory and safety assessments including cardiac biomarkers.

TERN-501 PK had low variability and was approximately dose-proportional from 3 mg to 60 mg following single doses and from 1 mg to 10 mg following multiple doses. Single-dose PK was predictive of multiple-dose PK with modest (< 2-fold) accumulation at steady state upon once daily dosing, consistent with the median half-life of approximately 14 to 21 hours following single or multiple doses. Urinary clearance appears to be a minor pathway of elimination of TERN-501, with a mean of < 3% of the dose excreted as unchanged TERN-501 in the urine.

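### SAP 7.17.4 sets BLQ plasma concentrations to 0 but plans geometric means, and gives no workable rule for a timepoint where only some values are BLQ

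*SAP*

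**What the plan says.** SAP 7.17.4 gives the rules for presenting plasma concentrations of TERN-501, TERN-101 and the metabolite TRN-000971. Four of them bear on this point.

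- Substitution: "Values that are BLQ will be set to 0 for the calculation of summary statistics". The number of BLQ values is also to be shown. No statistic is exempted from the zero.
- Graphs: "Individual patient and geometric mean concentration-time profiles, for each TERN-101 dose, will be presented graphically on linear and logarithmic concentration scales". These are for PK/PD sub-study patients on Day 1 and at Week 12.
- Display: "Arithmetic mean or median values that are BLQ will be presented as 0". This covers the arithmetic mean and the median, not the geometric mean.
- All-BLQ case: when every value is BLQ, the arithmetic statistics and order statistics are shown as zero, while "the geometric mean and geometric CV% will be denoted as NC". This shows that geometric mean and geometric CV% belong to the concentration summary. Apart from the general rule for fewer than three values, in which a BLQ result counts as a value, it is the only route to NC.

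Two neighbouring rules differ. For PK parameter generation, SAP 7.17.3 sets BLQ to 0 before the first measurable concentration, and "thereafter BLQ concentrations will be treated as missing". For the PD analytes 7αC4, FGF19 and bile acids, SAP 7.18 substitutes half the limit.

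**The concern.** A geometric mean is the exponential of the mean of the logarithms, and zero has no logarithm. The zero substitution suits arithmetic statistics but not geometric ones. The SAP acknowledges this when every value is BLQ, yet sends the mixed case through the zero rule.

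Three outcomes are then possible for one timepoint: a geometric mean of 0 (product form), an undefined value (log form), or a mean over the quantifiable patients only (log form with missing values dropped). The first two cannot be drawn on the planned logarithmic axis. The third departs from the written rule and is too high, because the patients with the lowest concentrations are the ones left out. Which one appears would be decided by programming, not by the SAP.

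At stake are the legibility and correctness of descriptive PK tables and figures that serve the exploratory PK objective.

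**Working it through.** The plan states no figure on this point, so there is none to reproduce. The check has three parts.

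**1. Which rule applies to a mixed timepoint**

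| Values at the timepoint | SAP 7.17.4 rule for the geometric mean |
|---|---|
| All quantifiable | Ordinary calculation |
| Some BLQ, three or more values in all | BLQ = 0, then calculate: no valid result |
| All BLQ | NC |
| Fewer than three values | NC |

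Only the second row fails. Day 1 pre-dose samples should all be BLQ and so fall in the third row. The exposed points are after the first dose: early samples, troughs, and the 48 and 72 h samples at Week 12.

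**2. What one BLQ value does**

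The example is illustrative: six patients (the approximate sub-study group size), assumed concentrations 2, 2.5, 3, 3.5 and 4 ng/mL, one BLQ value, and an assumed LLOQ of 1 ng/mL.

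Formulas: geometric mean = (product of x)^(1/n) = exp(mean of ln x); geometric CV% = 100 × √(exp(s²) − 1), where s² is the variance of ln x. The product of the five quantifiable values is 210.

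| Treatment of the BLQ value | Geometric mean | Geometric CV% |
|---|---|---|
| 0 (as written) | (210 × 0)^(1/6) = 0; log form undefined | not computable |
| Half the LLOQ | (210 × 0.5)^(1/6) = 2.17 | s² = 0.578, giving 88% |
| LLOQ | (210 × 1)^(1/6) = 2.44 | 53% |
| Dropped | 210^(1/5) = 2.91 | s² = 0.075, giving 28% |

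Under the zero rule the arithmetic mean is 15/6 = 2.5, so arithmetic summaries still work. Dropping the value gives a geometric mean 34% above the half-LLOQ result (2.91/2.17 = 1.34).

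**3. How often a mixed timepoint might occur**

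The documents give no LLOQ, so the BLQ rate p per sample is assumed, with samples treated as independent. P(at least one BLQ in n) = 1 − (1 − p)^n. For n = 6:

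- p = 2%: 1 − 0.98^6 = 11%
- p = 5%: 1 − 0.95^6 = 26%
- p = 10%: 1 − 0.90^6 = 47%
- p = 20%: 1 − 0.80^6 = 74%

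The chance that all six are BLQ is negligible at these rates, so these are in effect the chances of a mixed timepoint.

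On where it might occur, Protocol 2.2.1.2 describes TERN-501 accumulation as "consistent with the median half-life of approximately 14 to 21 hours following single or multiple doses". From 24 to 72 h, 2^(−48/14) = 9% to 2^(−48/21) = 21% of the concentration remains. Late samples are therefore the lowest in the profile, but without an LLOQ this does not show that any would be BLQ.

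**The case against.** The strongest reply is that little depends on these statistics. Several parts of it stand.

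- **Dose proportionality and elimination.** A reader might infer that the zero rule distorts the assessment of either. The documents do not support that. SAP 7.17 assesses them through AUC, Cmax, dose-normalised parameters, accumulation and linearity ratios, and half-life from individual log-linear fits. All of these follow SAP 7.17.3, where the zero rule of 7.17.4 plays no part. At most, the visual comparison of mean profiles is affected.
- **Visibility.** The BLQ count must already be shown, so a reader would see that such values exist. This tells the reader that a problem arose, but does not supply a usable geometric mean.
- **Group size.** With arms of 20, the formula gives 64% and 88% at BLQ rates of 5% and 10%. Those figures do not describe the profiles, which are confined to the sub-study. They could bear only on full-arm tables of sparse samples, where geometric statistics are implied rather than listed.
- **Analyte.** The profile sentence names only TERN-101 dose, whereas Protocol 9.4.4.2 plans mean profiles without that limit. The half-life above is for TERN-501 and cannot be carried over to TERN-101 or its metabolite. The gap exists whichever analyte is plotted.
- **PD convention.** Half the limit in SAP 7.18 applies to PD analytes measurable before any drug is given. A different rule for drug concentrations is not in itself an inconsistency.

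The reply does not remove the gap. The NC rule covers the all-BLQ case and very small series; a mixed series of three or more values remains without a valid geometric mean.

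**Conclusion.** The concern holds within a narrow scope. Whenever a timepoint with at least three values contains both BLQ and quantifiable results, SAP 7.17.4 as written gives a geometric mean of 0 or undefined and no geometric CV%. That follows from algebra and needs no assumption. If zeros are dropped in code, the value is biased upward; whether that would happen is not known from the documents.

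Frequency does rest on an assumption: 26% to 47% of groups of six for BLQ rates of 5% to 10% per sample, with independence between patients. No rate can be derived from the documents.

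The effect is confined to by-timepoint concentration summaries and the sub-study mean profiles. PK parameters and the primary and secondary efficacy conclusions are unchanged. The change is worth making because a planned output cannot be produced coherently as specified and the correction costs almost nothing.

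**What to change.** In SAP 7.17.4, limit BLQ = 0 to the arithmetic mean and SD, median, minimum and maximum. Then state one rule for the geometric mean, geometric CV% and geometric mean profiles when some values are BLQ. Either of these closes the gap:

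1. Set BLQ values after the first dose to half the LLOQ, including later pre-dose troughs, and keep NC when all values are BLQ. SAP 7.18 already uses this convention for PD concentrations.
2. Extend the existing NC rule to any timepoint that contains a BLQ value.

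The BLQ count is already required and needs no change.

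The cost is one sentence and one programming rule. Option 1 is an imputation convention, and in a group of six the choice of substitute moves the result (2.17 against 2.44 in the example). Option 2 imputes nothing but leaves gaps in the profile, most likely at its lowest points.
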